C.3.4. Study Arms: Control Arm: Participants in this arm will receive the traditional clinic intervention that focuses on testing services (National HIV & AIDS Strategic Plan 2016-2020). Currently, patients coming to the clinic receive testing and ART treatment as well as information about the disease management. Both children and caregivers receive this information.

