Treatment Arm 1 (G-CBT): In addition to usual care, children in this arm will receive a 10-session G-CBT for HIV/AIDS-associated stigma. While G-CBT has not been tested in SSA to reduce HIV/AIDS-associated stigma, it has been found effective in reducing self-stigma among adults with mental illness both in the U.S. and other countries.⁹⁷⁻⁹⁹ G-CBT has been widely used and found to be more effective than individual CBT on a range of mental disorders among children,¹⁰⁰⁻¹⁰³ including a potential low-cost alternative to individual therapy in developing countries where access to psychotherapy is scarce due to its high cost.¹⁰⁴⁻¹⁰⁵ G-CBT is likely to offer more opportunities for normalization, positive peer modeling, reinforcements, social support, exposure to social situations and feedback sources, given the context of shared experiences.¹⁰⁶⁻¹¹³ Within G-CBT, for stigma we will utilize core components of CBT (psychoeducation, cognitive restructuring, and skill-building to increase adaptive coping mechanisms):⁷⁹ 1) exploration of HIV's role and impact of stigma in CLWH's life; 2) use of cognitive restructuring to identify and address the negative stigma-associated beliefs, loss of self-worth, self-blame; and 3) skill-building around stress management and emotion-focused coping strategies to address negative feelings (e.g. assertiveness, relaxation skills and problem solving skills).¹¹⁴ CBT typically has a cognitive component which involves helping the person develop the ability to identify and challenge unrealistic negative thoughts, and a behavioral component to promote helpful behavioral responses.¹¹⁴ The research team will ensure: 1) 2) the developmental and cognitive adaptation of the content for children between 10-14 years, and 3) the cultural adaptation of the G-CBT to local context. Content will be tailored to match children's ability to comprehend and implement the therapeutic techniques, including age appropriate activities, child friendly materials, simplified language and visuals (e.g. cartoons),¹¹⁵ less complex behavioral techniques and more support, structure and feedback.¹¹⁶ In addition, the cultural adaptation is intended to enhance its treatment relevance, credibility, efficacy and effectiveness by aligning it to the socioeconomic situation, cultural beliefs, family, political and health systems in the region.¹¹⁷⁻¹¹⁸ G-CBT's cultural adaptation will be ensured by intensive consultative meetings with experienced in-country mental health workers and community leaders, led by in-country PI [name]. G-CBT will be facilitated by trained para-counselors selected using an agreed upon criteria with the community. They will participate in a 5-day training and receive monthly group supervision. Each group will have 10 participants and will last approximately 1 hour. Caregivers will not participate in G-CBT. Sessions will be delivered twice a week, outside of school hours.

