
Treatment Arm 2 (MFG): In addition to usual care, children-caregiver dyads in treatment arm 2 will receive the MFG intervention. Rooted in family systems theory, structural family theory and social learning theory with elements of psychoeducation and social group work, MFG is a family-centered, group-delivered, evidence informed, strength-based 10-session (weekly) intervention for children whose families struggle with poverty and associated stressors,^{78,85, 86, 89,119-123} and integrates components of existing evidence-based practices that successfully improve parental management, mental health promoting family processes, and family strengthening.¹²⁴⁻¹³¹ Specific MFG session content will draw on the current interventions implemented by ICHAD.^{132,133} Sessions will focus on the core components of MFG, also known as 4Rs and 2S's (rules, responsibility, relationships, respectful communication, stress and social support). Sessions focused on HIV and stigma will be adapted from our Suubi curriculum and resources from the Ministry of Health. The protocols have been designed to provide opportunities during each session to directly apply content to the realities of family life, emergent cultural and values perspectives, as well as tailor messages to age of child.⁸⁰ These will include group activities, role plays, sharing experiences and family take home activities. Families (children and caregivers) will be combined into groups to promote communication and support within and among families. Each group will have no more than 10 families. Parent peers (n=6) and community health workers (n=6) already trained in MFG delivery focused on child behavioral health used for the SMART Africa-Uganda study (U19MH110001) and Suubi4Her study (R01MH113486) will be invited to participate and receive a refresher training focused on *Suubi4Stigma*'s new content. During MFG implementation, facilitators will receive 2 hours per month of group supervision across sites. Given the significant and protective role families play in children's

health and mental health (section A.4.), we expect that strengthening family functioning and dialogue by involving caregivers through MFG will lead to better child outcomes, including HIV/AIDS-associated stigma. MFG sessions will last approximately 1 hour and will be delivered twice a week, outside of school hours.

Table 1. Variables and Instruments		Reliability	Time point
Variable	Measurement		
Demographics (Respondent: Adolescent)			

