Implementation/Evaluation. Having two facilitators per group will allow for detailed process notes on the implementation process and balancing “fidelity” and “fit” to local culture. Changes from the planned curriculum will be examined using process notes. Caregivers/children will report monthly on factors that affect their participation using an implementation checklist that assesses satisfaction and obstacles to program delivery: 1) factors interfering with youth or family participation (e.g. time, other priorities, stigma); 2) concrete obstacles (e.g. weather, transportation); and 3) site and staffing obstacles (e.g. time constraints).

C.3.6. Semi-structured Interviews (Aim 2). These interviews will: 1) Explore participants’ intervention experiences and perceived impact of the intervention on change mechanisms (including shared experiences, peer and family support, family communication, interpersonal and coping skills); and 2) Identify multi-level facilitators and barriers to G-CBT and MFG intervention, implementation and participation. Participants in the two treatment arms will be asked for feedback on intervention acceptability and relevance via semi-structured interviews upon intervention completion. Semi-structured in-depth interviews will be conducted with caregivers and CLWH separately at post intervention for each treatment arm. The interviews will provide rich data on participants’ processes and experiences with the program; processes behind key outcomes, mechanisms of change and mediating variables; and potential individual, family, contextual, programmatic, and structural factors affecting their experiences. At the end of the intervention, all facilitators will also be interviewed to gain a deeper understanding of implementation patterns and processes, including their views on sustainability. Interviews will be conducted in English or Luganda. Questions will be translated/back-translated by two team members fluent in both languages. Interviews will last about 1 hour and will be audio-taped.

C.3.6. Data Analysis

Aim 1: Feasibility and Acceptability. a) **Feasibility.** We will monitor recruitment rates and staff level of effort, number of screenings conducted, proportion eligible and agreed to enroll. Enrollment of 70% or higher will be

considered feasible.¹⁵⁹ We will also record the number of rescheduled, cancelled and missed sessions and assessments to inform estimation of staffing needs and retention protocols for a subsequent trial.

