b) *Acceptability.* We will adapt satisfaction surveys, (e.g., the Client Satisfaction Questionnaire (CSQ-8)) to assess acceptability.¹⁶⁰ Items include: "How satisfied were you with the program?", "How helpful was the program in addressing HIV-associated stigma?" and "How likely are you to recommend this program to other families with CLHA?" Given the modest sample size, quantitative analyses of intervention data will be largely descriptive and concentrate on tabulating and summarizing satisfaction outcomes. In regards to hypotheses and methods for primary preliminary/exploratory analyses *to assess study feasibility*, we expect that: **H1:** Following intervention, relative to the control group, participants in both treatment arms (G-CBT and MFG) will have: **H1a:** lower mean count of children reporting HIV/AIDS-associated stigma; **H1b:** lower mean levels of reported HIV/AIDS-associated stigma and improved child psychosocial functioning; **H1c:** lower mean levels of reported child mental health challenges; **H1d:** higher mean levels of adherence. **H2:** Following intervention, relative to the CBT intervention arm, participants in the MFG intervention will have: **H2a:** lower mean count of children reporting HIV/AIDS-associated stigma; **H2b:** lower mean levels of reported HIV/AIDS-associated stigma and improved child psychosocial functioning; **H2c:** lower mean levels of reported child mental health challenges; **H2d:** higher mean levels of adherence. Children will be the unit of analysis for these primary preliminary analyses. We will plot means by group over time to describe overall patterns of change. We will use linear mixed models (LMMs) to evaluate the proposed hypotheses. We will fit LMMs to ensure that all requisite information is available to perform the types of analyses typically undertaken in a formal RCT of intervention efficacy and to obtain valuable effect size information. LMMs will include random intercepts for clinic membership and random intercepts and slopes for subjects (three-level models). Due to the modest sample size, significance testing will be de-emphasized. Similarly, although the modest sample size precludes formal investigation of moderation, we will use the same LMM approach described above to compare children across study arms over time on the moderators listed in Table 1. Additional analyses will consider the role of child gender as a moderator in line with NIH guidelines addressing the importance of sex and gender as critical moderators. These moderation analyses will be secondary exploratory analyses. Additional exploratory analyses will study parents and children jointly as the unit of analysis via dyadic analysis methods such as actor-partner and means-and-deviation models to quantify parent vs. child stigma effects and between- vs. within-dyad effects on mental health outcomes.^{161,162}

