
Power Analyses. Although the study purpose is to determine preliminary feasibility and acceptability, rather than conduct formal hypothesis tests, we conducted several power analyses using NCSS PASS to supply additional information. Our power analyses assume $\alpha=.05$, power=.80, 81 participants retained at the final time point following 10% estimated attrition, and a clinic-based conservative unconditional ICC of 9.3% based on our previous SUUBI study of mental health in Uganda children.¹⁶³ For the target enrollment proportion of 70% to assess feasibility, the width to the limit of the confidence interval is 27.9% (standardized distance: .32). For continuous standard normal variables to assess acceptability (e.g., CSQ-8), the distance from the mean to the confidence limit is .30. These distances to confidence limits are between small (.20) and medium (.50) effect sizes. For preliminary efficacy exploratory analyses with two time points and paired comparisons of two out of the three groups at 81/3=27 participants per group (N=54 per comparison), minimum detectable standardized mean differences for continuous outcomes ranged from .79 to .97 for within-subjects correlations r ranging from .20 to .80. In sum, our study is powered to detect small-medium distances to confidence limits for descriptive statistics and large longitudinal analysis effects, though hypothesis testing is not the study focus.

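### The acceptability precision of .30 rests on all 81 retained participants, usual-care controls included; if only G-CBT and MFG participants rate the program, the same method gives about .37

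*Combined protocol and SAP*

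**What the plan says.** The Power Analyses paragraph (C.3.6 Data Analysis) sets common inputs for its figures: alpha .05, a clinic ICC of 9.3%, and "81 participants retained at the final time point following 10% estimated attrition". It later divides the 81 by three to get 27 per group, so the 81 covers all three arms. For acceptability it gives one figure: "For continuous standard normal variables to assess acceptability (e.g., CSQ-8), the distance from the mean to the confidence limit is .30". It places this distance between the small (.20) and medium (.50) benchmarks.

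Under Aim 1 b) Acceptability, the measure is an adapted satisfaction survey. One item reads "How helpful was the program in addressing HIV-associated stigma". The same paragraph says that "quantitative analyses of intervention data will be largely descriptive and concentrate on tabulating and summarizing satisfaction outcomes".

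Section C.3.4 describes what each arm receives:
- Control: "Participants in this arm will receive the traditional clinic intervention that focuses on testing services", together with ART and information on managing the disease.
- G-CBT: ten group sessions for the children. "Caregivers will not participate in G-CBT".
- MFG: "Families (children and caregivers) will be combined into groups to promote communication and support within and among families".

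The section on semi-structured interviews says: "Participants in the two treatment arms will be asked for feedback on intervention acceptability and relevance via semi-structured interviews upon intervention completion". The paragraph on data integration, at the end of the Aim 2 analysis, speaks of understanding satisfaction separately for each treatment arm.

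Nowhere does the plan say which arms complete the satisfaction survey, or whether children, caregivers or both do so.

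**The concern.** A satisfaction score for a stigma program can come only from people who were offered one. The only precision figure for acceptability uses a sample in which one participant in three received usual care. If those participants do not rate, the figure is too favourable. The Power Analyses paragraph names preliminary feasibility and acceptability as the purpose of the study, so this is the stated precision for one of its two main questions.

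**Working it through.** **Inputs.** Nine clinics with 10 children each (C.3.3), three clinics per arm (arm description before C.3.1), and 10% attrition, so 9 retained per clinic. The ICC is .093, alpha is .05, and the SD is 1 (standard normal score). Two-sided limits are assumed, because the plan does not state sidedness.

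**Formulas.**
- Design effect = 1 + (m − 1) × ICC = 1 + 8 × .093 = 1.744.
- Effective n = N / 1.744.
- Distance to limit = t(.975, effective n − 1) / √(effective n). The z form replaces t by 1.96.

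**Step 1: the plan's figure.** N = 81 gives effective n = 81 / 1.744 = 46.4. The distance is .295 (.297 with n rounded to 46), which rounds to .30. The z form gives .288.

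**Step 2: cross-check.** The same paragraph gives 27.9% for an enrollment proportion of 70%. An exact (Clopper-Pearson) 95% interval at .70 with n = 46 has full width .2791. Both printed figures fit one effective n, that of all three arms.

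**Step 3: other routes to .30.** Two were found that leave controls out, and each needs an input that the plan does not state.
- 54 children with a one-sided 5% limit: .296 (z) or .305 (t).
- 108 treatment-arm dyad members, 18 per clinic: design effect 1 + 17 × .093 = 2.581, effective n 41.8, distance .303 (z) or .312 (t). This has G-CBT caregivers rating sessions that they do not attend.

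On these bases the 70% proportion would have a width of 29% to 34%, not 27.9%.

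**Step 4: intervention arms only, by the method of Step 1.**

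| Base | Clinics | Effective n | t form | z form | t with clinics − 1 df |
|---|---|---|---|---|---|
| All 81 | 9 | 46.4 | .295 | .288 | .338 |
| 54, two programs pooled | 6 | 31.0 | .367 | .352 | .462 |
| 27, one program | 3 | 15.5 | .543 | .498 | 1.09 |

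Pooled over the two programs, the distance grows by .367 / .295 = 1.24, or about 24%.

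**Step 5: sensitivity.**
- *ICC for satisfaction (not given).* With 54 children the t form gives .273 at ICC 0, .295 at .02, .306 at .03 and .326 at .05. With 27 children it gives .478 at .05.
- *MFG caregivers also rate.* With an assumed within-dyad correlation of .093 to .5, the t form gives about .46 to .50 for MFG, and about .34 to .35 pooled with the G-CBT children.
- *No attrition.* 60 children give .357 (t) and 30 give .526 (t).

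**The case against.** **No arithmetic error.** A reader might infer that .30 is miscalculated. It is not: it follows from the stated inputs. What is in doubt is whether those inputs describe the people who rate.

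**The exclusion of controls is inferred.** The arm description speaks of treatment and control arms alike as delivered over three months, and C.3.4 calls usual care an intervention, so a survey of controls is conceivable. The interview sentence concerns a different instrument. The reference to intervention data is ambiguous, because it stands just before hypotheses that include the control group. This stands, and it is why the point is conditional. Against it are the item wording, the absence of any stigma program for controls, and the reference to satisfaction for each treatment arm.

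**One generic n may have served both figures.** Enrollment has its own denominator, yet the plan appears to use the same effective n of about 46 for it. One could read .30 as a decision to pool control ratings into acceptability. The documents do not show such a decision. They fit equally well with an illustrative figure computed once.

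**The replacement value is not fixed.** The 9.3% comes from a mental health study, and the ICC for satisfaction is unknown. At an ICC of .02 to .03, 54 children would give about .30. Caregivers may also rate. Both points stand, so .37 is the value at the plan's own ICC with child raters, not the only possible one.

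**Per-program precision was not promised.** It is tempting to say that the small-to-medium statement is false, or to prescribe .54 per program. The plan makes no per-program claim that could be false, and .54 ignores that each program has three clinics. Neither reading is supported.

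**Conclusion.** The point holds in conditional form and is minor. From the stated inputs, .30 is the precision for all 81 retained participants, including 27 usual-care controls. If the survey goes only to the G-CBT and MFG arms, which is the natural reading of its items, the comparable figure for 54 children is about .37 (.35 by z, about .46 with 5 clinic-level degrees of freedom). This rests on ICC .093, 9 retained per clinic, and one child rater per dyad.

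The small-to-medium description survives for the pooled estimate. It should not be carried over to each program: with 27 child raters at the plan's ICC the distance is about .5 at best (.50 z, .54 t), and about 1.09 if three clinics set the degrees of freedom.

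The consequence is limited. The satisfaction analysis is descriptive, and no threshold, test or go/no-go rule uses .30.

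**What to change.** - State which arms complete the satisfaction survey, who responds (children, caregivers or both), and at which time point.
- If it is the intervention arms, summarise satisfaction there without controls and replace .30 with the precision for that group: about .37 for 54 children pooled at ICC .093. If MFG caregivers also rate, recompute for that set of raters.
- Keep the small-to-medium statement for the pooled estimate only. If satisfaction is reported by program, say that precision is about .5 at best for 27 children, and much wider if the three clinics set the degrees of freedom.
- If controls are surveyed, .30 can stand, but say which program they rate.

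The cost is wording only. On the intervention-arm reading a stated precision becomes less favourable.

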C.2. Study Overview. *Suubi4Stigma*, a mixed-methods sequential explanatory study,⁹³ will address the urgent need for theoretically and empirically informed interventions that seek to reduce HIV/AIDS-associated stigma and its negative impact on child health and psychosocial well-being. We will test the feasibility, acceptability and preliminary effects of the G-CBT versus MFG intervention, two evidence-based interventions that have, to date, been extensively used to address mental health functioning among children and adolescents. Specifically, clinics will be randomized to one of three study arms (see C.3). The conceptual model (Fig 1) specifies the expected relationship between the intervention arms, mechanisms and potential outcomes.

Figure 2. *Suubi4Stigma* Assessment

usual (n=3 clinics; 30 child-caregiver dyads); 2) G-CBT intervention + usual care (n=3 clinics; 30 child-caregiver dyads); and 3) MFG intervention + usual care (n=3 clinics; 30 child-caregiver dyads). Both treatment and control arms will be delivered over a 3-month period. Data will be collected at baseline (pre-intervention), 3-months and 6-months post-intervention initiation. Children in the same clinic will be assigned to the same study condition to avoid contamination (Fig.2).

C.3.1 Study Inclusion/Exclusion Criteria: *Inclusion criteria for children:* The target population for this study is CLWH enrolled in care at a health clinic that has partnered with ICHAD ([name] et al.; *Suubi+Adherence* study). Child inclusion criteria are: 1) HIV+ status- defined as a child tested with confirmation by medical report and has been disclosed to; 2) prescribed ART; 3) living within a family (defined broadly - not necessarily with biological parents); and 4) ages 10 to 14. All eligible CLWH from a particular household will be enrolled in the study and will be assigned to the same study condition. *Inclusion criteria for parents/caregiving families.* Caregivers of CLWH who agree to participate in the study. *Exclusion criteria* includes a significant cognitive impairment of the child or parent that interferes with understanding the informed consent process. *Inclusion criteria for clinics.* Clinics registered and supported by the government to provide ART to CLWH in Masaka.

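### The minimum detectable differences of .79 to .97 do not carry 80% power for a time-averaged between-arm contrast with three clinics per arm; power there is about 57% to 66%

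*Combined protocol and SAP*

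**What the plan says.** The Power Analyses paragraph gives its inputs as a .05 significance level, "power=.80, 81 participants retained at the final time point following 10% estimated attrition", and a clinic ICC of 9.3%. For pairwise arm comparisons with two time points and 27 children per arm, it reports that "minimum detectable standardized mean differences for continuous outcomes ranged from .79 to .97 for within-subjects correlations r ranging from .20 to .80". It concludes that the study has power for "large longitudinal analysis effects, though hypothesis testing is not the study focus".

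C.2 Study Overview states that "clinics will be randomized to one of three study arms". The design description just before C.3.1 gives three clinics and 30 dyads to each arm, so 27 retained children per arm is 9 per clinic.

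Under Aim 1 of C.3.6 Data Analysis, children are the unit of analysis and "LMMs will include random intercepts for clinic membership and random intercepts and slopes for subjects (three-level models" (closing bracket omitted). No section states a degrees-of-freedom method or a small-sample correction for few clinics.

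**The concern.** A design effect puts the extra between-clinic variance into the standard error. It does not allow for that variance having to be estimated from very few clinics. With three randomised clinics per arm the reference distribution has 4 or 6 df, and its tails are much heavier than those of a t on about 50 df or a normal. A calculation that takes the ICC into the variance but counts children for the degrees of freedom gives detectable differences that are too small.

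There is a second, separate point. Averaging two measurements reduces child-level noise. It does not reduce a clinic effect that is the same at both times, which is what a random clinic intercept represents. Applying the averaging factor to the whole variance therefore shrinks the clinic part as well.

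At stake is whether the stated 80% power, and the summary that large effects are detectable, are accurate. A reader who carried the same method into the next trial would provide too few clinics.

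**Working it through.** **Inputs.** Significance level .05, power .80, ICC .093, 27 children per arm, two time points, r = .20 to .80 (Power Analyses). Three clinics per arm (design description before C.3.1), hence m = 27/3 = 9. SD = 1. Sidedness is not stated; two-sided reproduces the figures, whereas one-sided on 52 df gives .70 to .86.

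**Step 1: reproduce the plan's range.**

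- Design effect = 1 + (9 − 1)(.093) = 1.744.
- SE of a difference in two-time-point means = √[(2/27)(1.744)(1 + r)/2] = .278 (r = .20) and .341 (r = .80).
- Noncentral-t multiplier for 80% power on 54 − 2 = 52 df = 2.855.
- Detectable difference = .795 and .973, against the stated .79 and .97.

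**Step 2: is this the right contrast?** The stated range rises with r, in the ratio .97/.79 = 1.228. A time-averaged contrast gives √(1.8/1.2) = 1.225. A change score gives 2.0 and an ANCOVA 1.63, and both fall as r rises. With the design effect on 52 df, a change score would give 1.30 to .65 and an ANCOVA 1.01 to .62. Only the time-averaged contrast fits.

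**Step 3: was the ICC used?** Without it, 52 df gives .60 to .74, which does not match. The neighbouring precision figures also need it. Effective n = 81/1.744 = 46.4. An exact 95% interval at 70% is 27.9% wide at n = 46 but 20.9% at n = 81, and the plan states 27.9%. The half-width for a mean is about .30 at n = 46 but .22 at n = 81, and the plan states .30.

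**Step 4: clinic-level degrees of freedom.** A pairwise comparison has 6 clinics − 2 arms = 4 df. One model over all clinics has 9 − 3 = 6 df. The multipliers are 3.761 (4 df) and 3.367 (6 df), that is 1.32 and 1.18 times 2.855. Table rows A keep the SE of step 1.

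**Step 5: clinic effect stable over time.** Variance of a clinic mean = [(1 + r)/2 + 8(.093)]/9 = .1493 (r = .20) and .1827 (r = .80). SE = √[(2/3) × variance] = .316 and .349. Table rows B use these.

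| SE | df | Detectable difference, 80% power (r = .20 / .80) | Power at .79 / .97 |
|---|---|---|---|
| A: step 1 | 52 | .795 / .973 | 79.5% / 79.7% |
| A | 6 | .937 / 1.148 | 66.0% / 66.2% |
| A | 4 | 1.047 / 1.282 | 57.4% / 57.6% |
| B: stable clinic effect | 52 | .901 / .996 | 69.1% / 77.9% |
| B | 6 | 1.062 / 1.175 | 55.5% / 64.2% |
| B | 4 | 1.187 / 1.312 | 47.8% / 55.8% |

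A simulation of clinic means under B, tested with a clinic-level t-test, agrees with the 4 and 6 df rows to within half a percentage point, with type I error of about 5%.

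**The case against.** **The method is inferred.** The paragraph states neither contrast nor df, and other routes land on nearly the same values: z with the effective n rounded to 15 per arm (.792, .970); t on 30 df with 16 per arm (.793, .971); and 4 df with no design effect (.793, .971). This stands as a limit on saying what the authors did. It does not rescue the power. The first two ignore the number of clinics just as 52 df does. The third drops the ICC that the paragraph says it assumes and that 27.9% and .30 require. Rounding the effective n to 15 or 16 moves power only to 56%–59% (4 df) or 65%–68% (6 df).

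**The sums are right.** This is fair: each figure follows from its apparent formula. The fault lies in the df, and in shrinking the clinic variance, rather than in a slip of calculation.

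**The documents do not settle 4 against 6 df.** Also true, which is why both are shown. Neither gives 80%.

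**The summary sentence may hold for change over time.** With a clinic intercept and no clinic-by-time variation, the clinic effect cancels from change and child-level df are defensible: 2.855 × √[(2/27) × 2(1 − r)] = .98, .78 and .49 for r = .20, .50 and .80. So large change effects could be detectable at moderate or high r. But that range falls as r rises, and is not the one the plan reports.

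**Little depends on it.** The plan puts feasibility and acceptability first, de-emphasises significance testing, and does not derive the number of clinics or dyads from these figures. That limits the consequence; it does not make the stated power correct.

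**Conclusion.** The concern holds. For a time-averaged between-arm contrast, the only one tested whose dependence on r fits the published range, .79 to .97 are not detectable with 80% power. Correcting the degrees of freedom alone gives about 66% (6 df) or 57% (4 df), a shortfall of 14 to 23 percentage points. With the stable clinic effect of the planned model, power is 55% to 64% (6 df) or 48% to 56% (4 df). Even on 52 df that model has only 69% power at .79 with r = .20.

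This rests on the plan's own inputs: ICC .093, 9 retained children in each clinic and a two-sided .05 test. It also rests on the inferred time-averaged contrast, and it does not extend to change from baseline. Because the analyses are exploratory and no decision rule uses the range, this should be corrected but does not threaten the study's main purpose.

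**What to change.** In the Power Analyses paragraph:

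1. Name the contrast that .79 to .97 refers to and the degrees-of-freedom method.
2. If it is the time-averaged between-arm difference, restate the range on clinic-level df: .94 to 1.15 (6 df) or 1.05 to 1.28 (4 df). If the clinic effect is taken as stable over time, which matches the planned clinic intercept, use 1.06 to 1.18 (6 df) or 1.19 to 1.31 (4 df). Choose 6 df if one model covers all nine clinics, 4 df if the arms are analysed in pairs.
3. Amend the summary sentence to say that, for this contrast, only effects of roughly 1 SD or more are detectable with 80% power.
4. If a change-from-baseline (group-by-time) contrast is meant, compute it separately and state the assumption about clinic-by-time variation. The present range cannot stand for it, because a stable clinic effect cancels from change and the dependence on r reverses.

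The cost is text only. The stated figures become less favourable; clinics, children and the planned analysis are unchanged.
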